12.2.4 Duration of Response

Duration of response (DOR) is defined as the time from the date of achieving the first CR, CRi, nPR, or PR to the date of disease progression or death due to any cause, whichever comes first. Subjects who do not experience a disease progression or death will be censored using the same rule for PFS as described in Section 12.2.3.

DOR is calculated as date of disease progression or death (or censoring date for censored subjects) – date of achieving the first CR, CRi, nPR or PR + 1.

DOR will be analyzed similarly to PFS including a KM plot, as described in section 12.2.3.

12.2.5 Time to Response

The following time to response will be calculated and summarized using descriptive statistics.

- Time to CR = (date of CR – date of first dose +1)/30.4376
- Time to CR/CRi = (date of first CR or CRi – date of first dose +1)/30.4376
- Time to response of PR or better = (date of first PR or better – date of first dose + 1) / 30.4376

- Time to response of PRL or better = (date of first PRL or better – date of first dose + 1) / 30.4376

12.2.6 Time to Next Treatment (TTNT)

TTNT is defined as the time from the date of first dose to the date of institution of subsequent anticancer therapy for CLL or death due to any cause, whichever comes first. Subjects who do not have the above-specified events prior to the data cutoff date will be censored at the date of last visit. TTNT will be calculated as: (Earlier date of institution of subsequent anticancer therapy for CLL or death due to any cause) – date of first treatment + 1. For censored subjects, date of last visit will replace earlier date of use of subsequent anticancer therapy for CLL or death due to any cause in the calculation.

TTNT will be analyzed similarly to PFS including a KM plot, as described in section 12.2.3.

12.2.7 Overall Survival (OS)

Overall survival (OS) is defined as the time from the date of first dose to death due to any cause. Subjects who were not known to have died prior to the analysis data cutoff date will be censored as follows:

Situation	Outcome	Date	Event Description/ Censoring Reason
Death on or before data cutoff	Event	Date of death	Death
Exit study prior to data cutoff	Censored	Date of discontinuation from study participation as reported on study exit CRF	Withdrew consent/study terminated by sponsor/study exit
Lost to follow-up prior to data cutoff	Censored	Date subject last known to be alive	Lost to follow-up
No death reported on or before data cutoff	Censored	Date subject last known to be alive	Still on study

OS will be calculated as death date (or censoring date) – the date of first dose + 1.

OS will be analyzed similarly to PFS including a KM plot, as described in section 12.2.3.

12.2.8 Patient reported outcomes (PRO)

The patient reported outcomes include:

- The European Organization for Research and Treatment of Cancer (EORTC) Quality of Life Questionnaire (QLQ-C30) is a 30-item questionnaire designed to assess health-

related quality of life in cancer patients. There are 9 multi-item scales: 5 functional scales (physical, role, cognitive, emotional, and social); 3 symptom scales (fatigue, pain, and nausea and vomiting); and a global health and quality-of-life scale. Several single-item symptom measures are also included (dyspnea, insomnia, appetite, constipation, diarrhea, and financial impact).

- Medical outcomes Study Short Form 36 (SF-36) is used to assess health -related quality of life. It consists of eight scales (physical functioning, role-physical, bodily pain, general health perceptions, vitality, social functioning, role-emotional, and mental health) yielding two summary measures: physical and mental health

EORTC QLQ-C30 and SF36 will be collected at screening, Cycle 5, Cycle 9, Cycle 13, Cycle 18, Cycle 24 and end of study.

Cohorts 1 and 2:

Cohorts 1 and 2 collected EORTC QLQ-C30 and SF-36 and they are used to assess patient-reported quality of life.

Mean in mental/physical component scale for SF36, and each item of symptoms/functioning /global health status for EORTC QLQ-C30 is calculated at baseline and cycle 24. A repeated measures ANOVA is used to assess quality of life across the study period, using baseline and 24-month outcomes. Cohort (treatment-naïve and relapsed/refractory) is the factor used among patients to assess time-related outcomes and to determine any cohort, time, and interaction effects for individual patients.

The analyses were performed by Ohio State University Comprehensive Cancer Center and the results were published in the journal Cancer Discovery [5].

Cohorts 3 and 4:

Cohorts 3 and 4 collected EORTC QLQ-C30 only and is used to measure quality of life in cancer patients. The Sponsor will perform analysis to summarize EORTC QLQ-C30 for Cohorts 3 and 4.

The EORTC QLQ-C30 scale scores will be calculated using the EORTC QLQ-C30 Scoring Manual (Fayers & et al, 2001). The instrument yields the following scales:

- Global health status / Quality of Life (QoL) (2 items)
- Functional scales
 - Physical functioning (5 items)

- Role functioning (2 items)
- Emotional functioning (4 items)
- Cognitive functioning (2 items)
- Social functioning (2 items)
- Symptom scales / items
 - Fatigue (3 items)
 - Nausea and vomiting (2 items)
 - Pain (2 items)
 - Dyspnea, insomnia, appetite loss, constipation, diarrhea, Financial impact (1 item each)

The principle for scoring is the same for all scales. In brief, outcome scores are computed by standardizing the average of the items (i.e., a raw score) making up the scale. Outcome scores are computed using a linear transformation of the raw score such that scores range from 0 to 100. Details are provided in [Appendix E: Patient Reported Outcomes \(PRO\)](#). A higher score represents a higher ("better") level of functioning or a higher ("worse") level of symptoms; that is, a high score for a functional scale represents a high/healthy level of functioning, a high score for the GHS represents a high QoL, but a high score for a symptom scale/item represents a high level of symptomatology/problems. Note that the global health status scale is based on only the 2 specific HRQoL items and not the entire questionnaire.

If at least half the items of a scale are present for a time point, then the score will be calculated using the average of all items answered; otherwise, the score will be set to missing. For single measures, if the item is missing the scale score is set to missing.

Baseline is defined as the last available record on or prior to the start date of study treatment.

At each analysis visit and for cohort, the summary statistics (number of subjects, mean, standard deviation, median, and range) of scaled scores and changes from baseline scale scores will be calculated for global health status/QoL, each functional scale and each symptom scale by cohort at each analysis visit.

A listing of scale scores will be generated. A mean overtime plot will be generated for the global health status/quality of life. Also, the compliance to the schedule of administration will be summarized by cohort for baseline and post-baseline timepoints.

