- If there is a significant change, follow the process described in “Potential Hy’s Law Criteria Met” in this appendix for reporting PHL as an SAE.

LABORATORY TESTS

The list below represents a comprehensive list of follow-up tests that may aid in assessing PHL/HL.

Test results used to assess PHL/HL should be recorded on the appropriate eCRF.

Additional standard chemistry and coagulation tests	GGT LDH Prothrombin time INR
Viral hepatitis	IgM anti-HAV IgM and IgG anti-HBc HbsAg HBV DNA IgM and IgG anti-HCV HCV RNA IgM anti-HEV HEV RNA
Other viral infections	IgM and IgG anti-CMV IgM and IgG anti-HSV IgM and IgG anti-EBV
Alcoholic hepatitis	Carbohydrate deficient transferrin (CD-transferrin)
Autoimmune hepatitis	Antinuclear antibody (ANA) Anti-Liver/Kidney Microsomal Ab (Anti-LKM) Anti-Smooth Muscle Ab (ASMA)
Metabolic diseases	Alpha-1-antitrypsin Ceruloplasmin Iron Ferritin Transferrin Transferrin saturation

Reference

FDA Guidance for Industry (issued July 2009). Drug-induced liver injury: Premarketing clinical evaluation <https://www.fda.gov/regulatory-information/search-fda-guidance-documents/drug-induced-liver-injury-premarketing-clinical-evaluation>.

Table 15: Chronic Lymphocytic Leukemia Health-Related Quality of Life and Emotional Distress Assessment

	Screening		Cycle 1, Day 1 (Only if not finished from screening).	Cycle 2, 3, 4, Day 1	Cycle 5, Day 1	Cycle 6, 7, 8, Day 1	Cycle 9 Day 1	Cycle 10, 11 Day 1	Cycle 12, Day 1 (Cycle 13 Day 1 for Cohorts 3 and 4)	Cycle 18 Day 1 (Cycle 19 Day 1 for Cohorts 3 and 4)	Cycle 24 Day 1	End of Study (36 months complete or off prior to this)
Charlson Comorbidity Index (Completed by Study Personnel)	x	x										
Sociodemographics	x	x							x		x	x
Life Events	x	x							x		x	x
Social Support	x	x		x		x		x	x	x	x	x
Social Contacts	x	x						x	x	x	x	x
Patient Health Questionnaire (PHQ-9)	x	x						x	x	x	x	x
Impact of Events	x	x		x		x		x	x	x	x	x
Feelings in the Past Month (SF-36)	x	x		x		x		x	x	x	x	x
EORTC-QLQ-C30 Questionnaire	x	x		x		x		x	x	x	x	x
GAD-7 Questionnaire	x	x						x	x	x	x	x
Anxiety (STAI)	x	x		x		x		x	x	x	x	x
Depressive Symptoms (CES-D)	x	x		x		x		x	x	x	x	x
Perception of CLL	x	x		x		x		x	x	x	x	x
Fatigue	x	x	x	x	x	x	x	x	x	x	x	x
Moods (POMS)	x	x	x	x	x	x	x	x	x	x	x	x
Sleep	x	x	x	x	x	x	x	x	x	x	x	x
Pain	x	x	x	x	x	x	x	x	x	x	x	x

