2.0 Study Objectives

The primary objectives are:

Cohort 1 and 2:

- To determine the overall response rate (ORR) at 12 months with the combination of acalabrutinib plus obinutuzumab in subjects with relapsed or refractory chronic lymphocytic leukemia (CLL)
- To determine the ORR at 12 months with the combination of acalabrutinib plus obinutuzumab in subjects with treatment-naïve CLL
- To establish the safety and feasibility of the combination of acalabrutinib plus obinutuzumab

Cohort 3 and 4:

- To establish the safety of the combination of acalabrutinib plus rituximab plus venetoclax in subjects with relapsed or refractory CLL (Cohort 3)
- To establish the safety of the combination of acalabrutinib plus obinutuzumab plus venetoclax in subjects with treatment-naïve CLL (Cohort 4)

[figure not shown]
The secondary objectives are:

- To determine the complete response (CR) rate and minimal residual disease (MRD)-negative CR rate in subjects with previously untreated and relapsed and refractory CLL with these regimens (all cohorts)

- To evaluate the ORR of the combination therapy of acalabrutinib plus venetoclax plus an anti-CD20 antibody(rituximab or obinutuzumab) at Cycle 16 (Cohorts 3 and 4)
- To determine the time to response, duration of response (DOR), progression-free survival (PFS), time to complete response (CR), time-to-next treatment (TTNT), and overall survival (OS) with these regimens (all cohorts)
- To assess for serial development of resistance by baseline and longitudinal assessment of mutations of Bruton tyrosine kinase (BTK) and phospholipase C gamma 2 (PLCG2) at regular follow-up intervals and by examining diagnosis to relapse samples by whole-exome sequencing (all cohorts)
- To determine trajectory of psychological and behavioral responses to acalabrutinib and covariation with response to therapy (all cohorts)
- To determine the pharmacokinetics of orally administered acalabrutinib (all cohorts) and venetoclax (Cohorts 3 and 4)

The exploratory objectives are:

CCI

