7.4 Missing Data Handling

No imputation for missing values of efficacy endpoints. Imputation for missing dates such as AE start or end dates and prior and concomitant medication start dates or end dates will be documented in the programming specifications.

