15.0 APPENDICES

Appendix A: Analysis Windows

Tumor assessment/CT/SPD For Cohort 1 and 2				
			Analysis Window (Study Day)	
Nominal Visit	Study Day	Nominal Month	Lower (inclusive)	Upper (inclusive)
C4D1	85	0		127
C7D1	169	1	128	211
C10D1	253	1	212	281
C12D1	309	1	282	351
C15D1	393	13	352	435
C18D1	477	15	436	519
C21D1	561	18	520	603
C24D1	645	21	604	687
C30D1	813	27	688	855
C36D1	981	32	856	

Tumor assessment/CT/SPD For Cohort 3 and 4				
			Analysis Window (Study Day)	
Nominal Visit	Study Day	Nominal Month	Lower (inclusive)	Upper (inclusive)
C4D1	85	0		127
C7D1	169	1	128	211
C10D1	253	1	212	295
C13D1	337	1	296	379
C16D1	421	13	380	463
C19D1	505	15	464	547
C22D1	589	18	548	617
C24D1	645	21	618	687
C30D1	813	27	688	855
C36D1	981	32	856	

Hematology / Chemistry				
			Analysis Window (Study Day)	
Nominal Visit	Study Day	Nominal Month	Lower (inclusive)	Upper (inclusive)
C1D1	1	0		1
C1D8	8	1	2	12
C1D15	15	1	13	21
C2D1	29	1	22	43
C3D1	57	2	44	71
C4D1	85	2	72	99
C5D1	113	3	100	127
C6D1	141	4	128	155
C7D1	169	5	156	183
C8D1	197	6	184	211
C9D1	225	7	212	239
C10D1	253	8	240	267
C11D1	281	9	268	295
C12D1	309	10	296	351
C15D1	393	13	352	435

C18D1	477	15	436	519
C21D1	561	18	520	603
C24D1	645	21	604	687
C30D1	813	27	688	855
C36D1	981	32	856	

Physical Examination/ECOG				
			Analysis Window (Study Day)	
Nominal Visit	Study Day	Nominal Month	Lower (inclusive)	Upper (inclusive)
C1D1	1	0		1
C1D8	8	1	2	12
C1D15	15	1	13	21
C2D1	29	1	22	43
C3D1	57	2	44	71
C4D1	85	2	72	99
C5D1	113	3	100	127
C6D1	141	4	128	155
C7D1	169	5	156	183
C8D1	197	6	184	211
C9D1	225	7	212	239
C10D1	253	8	240	267
C11D1	281	9	268	295
C12D1	309	10	296	351
C15D1	393	13	352	435
C18D1	477	15	436	519
C21D1	561	18	520	603
C24D1	645	21	604	687
C30D1	813	27	688	855
C36D1	981	32	856	

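### The Cohort 1 and 2 quality-of-life analysis uses baseline and Cycle 24 only, so it cannot show the trajectory that the secondary objective asks for

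*SAP*

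**What the plan says.** The secondary objective, worded alike in protocol 1.2 and SAP 2.0, is "To determine trajectory of psychological and behavioral responses to acalabrutinib and covariation with response to therapy (all cohorts".

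SAP 12.2.8 gives one collection schedule: "EORTC QLQ-C30 and SF36 will be collected at screening, Cycle 5, Cycle 9, Cycle 13, Cycle 18, Cycle 24 and end of study". Protocol Table 15 has Cycle 12 in place of Cycle 13 for Cohorts 1 and 2, and keeps Cycle 13 for Cohorts 3 and 4.

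For Cohorts 1 and 2, the mean of each scale "is calculated at baseline and cycle 24". The model follows: "A repeated measures ANOVA is used to assess quality of life across the study period, using baseline and 24-month outcomes", with cohort, time and their interaction as effects. The SAP adds that the site has already done and published these analyses.

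For Cohorts 3 and 4, the same section plans scores and changes from baseline at each analysis visit, a mean-over-time plot for global health status, and a summary of compliance with the questionnaire schedule.

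On missing data, SAP 7.4 states "No imputation for missing values of efficacy endpoints". The scoring rule, which begins "If at least half the items of a scale are present for a time point", covers missing items within a form. It does not cover a missed form.

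**The concern.** A trajectory needs the scores between the two ends. An early dip followed by recovery, a steady rise, and a rise followed by a fall can all give the same change from baseline to Cycle 24. The forms that would tell these apart are scheduled, but this analysis does not use them.

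The choice also affects who informs the result. SAP 12.2 assigns the secondary efficacy analyses to the All Treated Population, and 12.2.8 sits under that heading. An estimate of change built on two time points draws its within-subject information only from subjects who have both forms. Those who left before Cycle 24 may differ from those who stayed.

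The SAP also handles the cohorts unequally: the 24 planned subjects in Cohorts 3 and 4 get a by-visit description, and the 45 in Cohorts 1 and 2 do not. The objective is the same for both groups.

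**Working it through.** The documents give no sample size, effect size, standard deviation or expected dropout for this analysis, so there is no stated figure to reproduce.

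**1. Visits used.** Through Cycle 24 the SAP lists five post-baseline assessments: Cycles 5, 9, 13, 18 and 24. One is analysed, so 4/5 = 80% are unused. Adding end of study gives six, so 5/6 = 83% are unused. Of all seven collection points, two are used.

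**2. Time label.** With 28-day cycles, Cycle 24 Day 1 is 23 × 28 + 1 = day 645, and 645/30.4375 = 21.2 months. The SAP Appendix A row "C24D1 645 21 604 687" agrees (nominal month 21). That row comes from tables for other assessments; Appendix A has no window for questionnaires. Twenty-four months is 24 × 30.4375 = day 730.5, close to Cycle 27 Day 1 (26 × 28 + 1 = day 729). The SAP lists no questionnaire there.

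**3. Complete pairs.** Planned numbers are 26 (Cohort 1) and 19 (Cohort 2), from SAP 4.0. If a share d of subjects lacks a Cycle 24 form, the pairs left are N × (1 − d). The values of d are assumptions.

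| d | Cohort 1 | Cohort 2 | Both |
|---|---|---|---|
| 10% | 23.4 | 17.1 | 40.5 |
| 20% | 20.8 | 15.2 | 36.0 |
| 30% | 18.2 | 13.3 | 31.5 |
| 40% | 15.6 | 11.4 | 27.0 |

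**4. Possible bias.** An illustrative simulation used 45 subjects, a standard deviation of 20, a between-visit correlation of 0.6, a true change of +7.0 and dropout more likely after a low score. It compared subjects with both forms against maximum likelihood on all visits through Cycle 24, with 200 replicates per row. Every input is an assumption.

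| Missing at Cycle 24 | Pairs only | All visits |
|---|---|---|
| 10% | 6.93 | 7.16 |
| 19% | 6.63 | 7.02 |
| 32% | 6.49 | 6.89 |
| 44% | 6.06 | 6.89 |

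The simulation error of the pairs-only means is about 2.68/√200 = 0.19 in the first row and 3.55/√200 = 0.25 in the last. Up to about 30% missing, the pairs-only shift is therefore roughly 0.1 to 0.5 points and hard to tell from simulation noise in the first two rows. Where it is visible, it understates the improvement. Another dropout mechanism could give another size or sign.

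**5. Number of scales.** The QLQ-C30 yields 1 global + 5 functional + 3 symptom + 6 single-item = 15 scales. Two SF-36 component scores make 17.

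**The case against.** The strongest reply is that this analysis is finished. The SAP records it as performed and published by the site, the sponsor's own questionnaire analysis covers Cohorts 3 and 4 only, and SAP 7.1 plans no formal hypothesis tests. A new model would be post hoc. That stands, and it fixes the status of any addition: supplementary and descriptive. It does not make two points into a trajectory.

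A reader might infer several stronger things that the documents do not support.

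- *That early leavers are excluded from the analysis.* The SAP does not say how a missing Cycle 24 form is handled or how the ANOVA was fitted. A mixed-model fit would keep subjects who have only a baseline form, though they would still add nothing to the within-subject change.
- *That the result is tilted toward patients doing well.* No document gives a missingness rate, and the illustration above moved slightly the other way.
- *That the whole objective is unanswered.* Cohorts 3 and 4 have by-visit outputs, so the trajectory gap concerns Cohorts 1 and 2.
- *That covariation with response is certainly unplanned.* The visible text has no such analysis, but protocol 14.6.2 ends in redacted text, so only the visible text can be called silent.
- *That an all-visit model of these two questionnaires would settle the objective.* Psychological responses are also measured by the CES-D, PHQ-9, STAI, GAD-7, POMS and Impact of Events Scale, which the SAP's questionnaire section does not analyse.

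The 21- versus 24-month mismatch is real, but it is a matter of wording.

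**Conclusion.** The point holds for Cohorts 1 and 2. The plan analyses one of five scheduled post-baseline assessments through Cycle 24 and so cannot describe the trajectory named in the objective. This follows from the text and rests on no assumption.

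The possible bias is a weaker statement. A subject without a Cycle 24 form does not inform the estimated change, and the estimate may be biased as a result. The documents give neither the size nor the direction. The counts of lost pairs (4.5 to 13.5 of 45 at 10% to 30% missing) depend on the assumed rates.

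This is a worthwhile, inexpensive improvement to a descriptive secondary analysis. The primary endpoint is not affected.

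**What to change.** Add to SAP 12.2.8 a supplementary analysis for Cohorts 1 and 2, labelled post hoc to the published one:

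- **Minimum.** Produce the outputs already specified for Cohorts 3 and 4: scores and changes from baseline by visit, the mean-over-time plot and the compliance table. State the questionnaire visit windows, and settle Cycle 12 versus Cycle 13 against protocol Table 15.
- **Preferably.** Fit a likelihood-based mixed model to the common visits from baseline through Cycle 24, with visit, cohort and visit-by-cohort, and a simple structured covariance because there are only 45 subjects. It relies on missingness being explained by the observed scores, which should be stated.
- **End of study.** Report these forms separately by actual date. Table 15 places them at 36 months or at earlier exit, so they do not share a visit time.
- **Covariation with response.** Show by-visit scores by response status. Entering post-baseline response as a covariate would be hard to interpret, and there may be few non-responders: at the design targets of 75% (relapsed/refractory) and 80% (treatment-naive), 26 × 0.25 + 19 × 0.20 = 10.3 of 45. Otherwise, state that this part of the objective is not addressed.
- **Other psychological instruments.** Analyse them, or state that they are not addressed.
- **Label.** Reconcile Cycle 24 with the 24-month wording.

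The cost is modest programming across about 17 scales on forms already scheduled, with no new procedures for subjects. The result remains supplementary and descriptive.

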13.0 Safety Analyses

Safety analyses will be performed using the All Treated Population unless specified otherwise.

Safety will be assessed by evaluation of treatment-emergent adverse events (TEAEs), laboratory values, vital signs measurements, electrocardiogram (ECG) results, physical examinations, and Eastern Cooperative Oncology Group (ECOG) performance status.

13.1 Adverse Events

AEs will be coded using the Medical Dictionary for Regulatory Activities (MedDRA v 24.0) reporting system. The investigator will grade AEs according to the National Cancer Institute Common Terminology Criteria for Adverse Events (NCI-CTCAE) v4.03 for AEs.

Hematologic toxicity is assessed by the investigator according to IWCLL 2008 guidelines for Cohorts 1 and 2, and NCI CTCAE v4.03 for Cohorts 3 and 4. TEAEs are defined as those events that occur on or after the first dose of study drug, through the treatment phase, and within 30 days following the last dose of study drug.

All TEAEs will be summarized by cohort as treated. For each cohort, AE incidence rates will be summarized with frequency and percentage by system organ class and preferred term, and the denominator for the AE incidence rate will be based on the number of subjects treated in that cohort unless otherwise specified. In addition, AE incidence rates will also be summarized by severity, and relationship to study drug. Relationship to study drug, per the investigator's judgment, is recorded on the CRF.

Subjects with multiple occurrences of events for a given preferred term, system organ class, or overall will be counted only once at the maximum severity, and strongest relationship to study drug for each preferred term, system organ class, and overall, respectively.

Summaries will be presented for:

- treatment-emergent AEs
- treatment-emergent serious adverse events (TESAEs)
- treatment-related TEAEs
- treatment-related TESAEs
- AEs leading to study drug discontinuation or dose modifications or dose delay
- treatment-emergent fatal (Grade 5) AEs

13.2 Adverse Events of Clinical Interest.

Adverse events of clinical interest (ECIs) are specified in Appendix F. Subject incidence rates of AEs of clinical interest will be summarized similarly to TEAEs by cohort.

